6.2.5.1 Follow-up for dose-limiting toxicities

Patients whose treatment is discontinued or interrupted due to a DLT, must be followed until resolution or stabilization of the DLT event, whichever comes first, as described in [Section 6.3.1](#).

In case of a hemorrhagic event, of any grade (CTCAE grade 1 included), the Investigator is advised to perform coagulation tests and an albumin assessment.

Additional guidance on the management of grade 4 thrombocytopenia and grade 4 neutropenia is described in [Section 6.3.2](#).

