If a patient requires a dose delay from either study drug of > 21 days due to an LDE225 or INC424 related toxicity, then the patient must be discontinued from the study; however, if the patient is obtaining clinical benefit in terms of response, the patient may continue treatment at the same or at a reduced dose following discussion between the investigator and Novartis. All patients will be followed for AEs and SAEs for 30 days following the last dose of LDE225 and/or INC424.

Dose modifications for toxicities occurring during the DLT-definition period (6 weeks or 42 days) will not be allowed unless the toxicity qualifies as a DLT. After a toxicity has been characterized as a DLT, a patient can resume therapy with a reduced treatment dose according to the guidelines provided in [Section 6.2.5.1](#).

If the administration of study treatment was interrupted for reasons other than toxicity, then treatment with LDE225 and INC424 may be resumed at the same dose.

Patients who experience muscle toxicity, regardless of whether the toxicity meets the criteria described for a DLT, should be followed according to the dosing modifications for LDE225 as per [Table 6-5](#).

Patients who experience hematologic, renal, or hepatic toxicities should receive follow up evaluations as outlined in [Table 6-7](#).

All interruptions or changes to study drug administration must be recorded on the Dosage and Administration Record eCRF.

[figure not shown]

Table 6-4 Criteria for interruption and re-initiation of INC424 and LDE225 treatment

| | |
|--|---|
| Dose modifications for toxicities occurring during the DLT-definition period (6 weeks or 42 days), and considered as treatment-related, will not be allowed until the toxicity qualifies as a DLT. | |
| Worst toxicity (CTCAE 4.03 Grade) | Dose Modifications for INC424 and LDE225 |
| HEMATOLOGICAL | |
| Neutropenia (ANC) (for 2 consecutive assessments within 48 hrs except febrile neutropenia) | |
| Grade 1 (ANC < LLN - $1.5 \times 10^9/L$) Grade 2 (ANC < $1.5 - 1.0 \times 10^9/L$) Grade 3 (ANC < $1.0 - 0.5 \times 10^9/L$) | INC424: Maintain dose level LDE225: Maintain dose level |
| Grade 4 (ANC < $0.5 \times 10^9/L$) | INC424: Hold dose until resolved to \leq grade 1, then maintain dose level LDE225: Hold dose until resolved to \leq grade 1, then maintain dose level |

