| Asymptomatic or Symptomatic CK elevation | |
| Grade 3 or 4 without renal impairment [Grade 3 (CK elevation $>5 \times$ ULN - $10 \times$ ULN)] [Grade or 4 (CK elevation $>10 \times$ ULN)] | 
 Interrupt treatment and monitor CK levels weekly until resolution to baseline level. Monitor muscle symptoms for changes until resolution to baseline. Check renal function (serum creatinine) regularly and ensure that patient is adequately hydrated. If renal function is not impaired (normal serum creatinine) and CK resolves to baseline level, consider resuming treatment at a reduced dose. CK levels should be measured weekly for 2 months after re-administration of sonidegib and monthly thereafter. |
| Grade 3 or 4 with renal impairment | 
 Interrupt treatment and monitor CK levels weekly until resolution to baseline level. Monitor muscle symptoms for changes until resolution to baseline. If renal function is impaired ($\geq 50\%$ above the baseline level), interrupt treatment. Ensure patient is adequately hydrated and evaluate other secondary causes. Continue monitoring of CK and creatinine levels weekly. If CK levels return to baseline level and creatinine levels return to baseline, consider resuming treatment at the reduced dose otherwise discontinue treatment permanently. |

Table 6-6 Dose restart guidelines and allowed maximum doses for patients who have previously interrupted dose for grade 4 thrombocytopenia and grade 4 neutropenia

[figure not shown]
| Current PLT Count | ▼ Dose Restart or Dose Increase Guidelines ▼ | |
|-----------------------------------|--|--------------------------------|
| | INC424 | LDE 225 |
| < 50 x10 ⁹ /L | Continue to hold | Continue to hold |
| 50 to < 75 x10 ⁹ /L | Restart at 5 mg BID for at least 14 days If stable, may increase to 10 mg BID or original dose (whichever is lower) | Restart at original dose level |
| 75 to < 100 x10 ⁹ /L | Restart at 10 mg BID for at least 14 days If stable, may increase to 15 mg BID or original dose, (whichever is lower) | Restart at original dose level |
| 100 to < 125 x10 ⁹ /L | Restart at original dose | Restart at original dose level |
| ≥ 125 x10 ⁹ /L | Restart at original dose | Restart at original dose level |
| Current ANC Level | ▼ Dose Restart or Dose Increase Guidelines ▼ | |
| < 0.5 x10 ⁹ /L | Continue to hold | Continue to hold |

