| 0.5 to < 0.75 x10 ⁹ /L | 5 mg BID for at least 2 weeks; if stable, may increase to 10 mg BID or original dose, (whichever is lower) | Restart at original dose level |
| 0.75 to <1 x10 ⁹ /L | 10 mg BID for at least 2 weeks; if stable, may increase to 15 mg BID or original dose, (whichever is lower) | Restart at original dose level |
| 1 to < 1.5 x10 ⁹ /L | Restart at original dose | Restart at original dose level |
| ≥ 1.5 x10 ⁹ /L | Restart at original dose | Restart at original dose level |

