6.3.2.1 Management of thrombocytopenia

It is recommended that patients who are dose reduced for thrombocytopenia have more frequent hematology assessments. Platelet counts must be obtained at least weekly for 4 weeks, and then at least every second week for the next 4 weeks. Thereafter, they may resume normal scheduled evaluations.

Dose escalation guidelines which allow maximum doses for patients who have previously decreased dosing for thrombocytopenia are described in [Table 6-6](#).

In the case of grade 4 thrombocytopenia, assessment of platelet count is recommended to be repeated twice weekly, until resolution to grade \leq 3 thrombocytopenia.

Dose restart guidelines and allowed maximum doses for patients who have previously interrupted dose for grade 4 thrombocytopenia can be found in [Table 6-6](#).

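### Restart doses after grade 4 thrombocytopenia differ between Protocol Tables 6-4 and 6-6, and Table 6-4 also disagrees with the hepatic stop rule and the dose floor

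*Protocol*

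**What the plan says.** **Restart after grade 4 cytopenia.** In Protocol Table 6-4 (Section 6.3.1), the grade 4 neutropenia and grade 4 thrombocytopenia rows hold both drugs until recovery to at most "grade 1, then maintain dose level". By that table's own bands, this means ANC ≥1.5 or platelets ≥75 (all counts here are x10⁹/L).

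Table 6-6, in the same section, is titled "Dose restart guidelines and allowed maximum doses for patients who have previously interrupted dose for grade 4 thrombocytopenia and grade 4 neutropenia". For INC424 it gives:
- platelets 50 to <75: "Restart at 5 mg BID for at least 14 days"
- platelets 75 to <100: "Restart at 10 mg BID for at least 14 days"
- ANC 0.5 to <0.75: "5 mg BID for at least 2 weeks; if stable, may increase to 10 mg BID or original dose"

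LDE225 restarts at its original level in every band where restart is allowed.

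**Signposts.** Section 6.3.1 says that after a DLT "a patient can resume therapy with a reduced treatment dose according to the guidelines provided in" Section 6.2.5.1. That section says "Additional guidance on the management of grade 4 thrombocytopenia and grade 4 neutropenia is described in" Section 6.3.2. Section 6.3.2.1 then says "Dose restart guidelines and allowed maximum doses for patients who have previously interrupted dose for grade 4 thrombocytopenia can be found in" Table 6-6, and Section 6.3.2.2 does the same for neutropenia. Section 6.2.5, however, sends DLT patients to Section 6.3.1 and Table 6-4.

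**Grade 4 AST/ALT.** Without bilirubin above 2 x ULN, Table 6-4 holds both drugs and resumes them at lower doses. Sections 6.2.5 and 7.1.3 require discontinuation for grade 4 non-hematologic toxicity, and Table 6-3 lists grade 4 AST/ALT under that heading.

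**Dose floor.** Dose level -1 (INC424 10 mg BID with LDE225 200 mg QD) is the lowest level allowed in Section 6.3.1, Section 7.1.3 and the Table 6-2 footnote. The only exception is for thrombocytopenic DLTs in Cohort 1. Table 6-4 nevertheless reduces INC424 to 5 mg BID for any grade 3 thrombocytopenia.

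**The concern.** These are the dosing instructions after severe toxicity, so the stake is patient safety and consistent dosing. A site that reads only the Table 6-4 row for grade 4 thrombocytopenia resumes full dose at a platelet count where Table 6-6 prescribes a lower one. Neither table is uniformly the more cautious. Table 6-6 gives less INC424 at platelets 75 to <100, while Table 6-4 holds longer at platelets 50 to <75 and at ANC 0.5 to <1.5. A general habit of following one table therefore does not always give the safer dose. In the hepatic case the same event can be read as a permanent stop or as a hold followed by resumption.

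**Working it through.** There is no planned figure to reproduce. The check applies both tables to the same counts.

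**Inputs.** D is the patient's original INC424 dose in mg BID. The recommended Phase II dose is D = 20 with LDE225 400 mg QD (Amendment 2 rationale).
- Table 6-4 restart dose: D if platelets ≥75 (or ANC ≥1.5); otherwise hold.
- Table 6-6 restart dose: hold if platelets <50 (ANC <0.5); 5 at platelets 50 to <75 (ANC 0.5 to <0.75); min(10, D) at platelets 75 to <100 (ANC 0.75 to <1); D above that.

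**Result at D = 20 (INC424, mg BID):**

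| Count | Table 6-4 | Table 6-6 | Agree? |
|---|---|---|---|
| Platelets <50 | hold | hold | yes |
| Platelets 50 to <75 | hold | 5 | no |
| Platelets 75 to <100 | 20 | 10 | no |
| Platelets 100 to <125 | 20 | 20 | yes |
| Platelets ≥125 | 20 | 20 | yes |
| ANC <0.5 | hold | hold | yes |
| ANC 0.5 to <0.75 | hold | 5 | no |
| ANC 0.75 to <1 | hold | 10 | no |
| ANC 1 to <1.5 | hold | 20 | no |
| ANC ≥1.5 | 20 | 20 | yes |

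The tables differ in 2 platelet bands and 3 ANC bands, 5 of 10. The five are not equal in kind. In four of them one table holds and the other permits a restart; LDE225 there is 0 versus 400 mg/day. Only at platelets 75 to <100 do both tables give a drug dose, and the doses differ:
- D = 20: 2 x 20 = 40 versus 2 x 10 = 20 mg/day
- D = 15: 30 versus 20 mg/day
- D = 10: 20 versus 20 mg/day, no difference

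If the patient is stable after at least 14 days in that band, Table 6-6 allows the lower of 15 mg BID and D. The gap then closes for D = 15 but remains 40 versus 30 mg/day for D = 20.

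**Grade 4 AST/ALT.** Section 6.2.5 first allows resumption under Section 6.3.1 and Table 6-4, then lists DLTs for which the patient must nonetheless stop permanently. Grade 4 non-hematologic toxicity is on that list, and Section 7.1.3 repeats it without qualification. On that reading the Table 6-4 row can never apply. Yet Table 6-4 gives this event its own resumption row and limits its generic grade 4 stop to other non-hematological events.

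**Dose floor.** Compare the two components with level -1 (10 mg BID, 200 mg QD):
- Patient on 20 mg BID + 400 mg QD with grade 3 thrombocytopenia: moves to 5 mg BID + 400 mg QD. INC424 is below level -1 and LDE225 above it, so the combination is not plainly below the floor.
- Patient already at 10 mg BID + 200 mg QD: moves to 5 mg BID + 200 mg QD. One component is lower and the other equal, so this is below the floor.

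The Cohort 1 exception does not cover the second case generally. Grade 3 thrombocytopenia is not a DLT in Table 6-3, and the exception names only Cohort 1.

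**Febrile neutropenia (minor).** Section 6.2.5 lists only a second episode for permanent stop; Table 6-4 and Section 7.1.3 stop at any episode. Stopping at the first satisfies all three.

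**Frequency.** Section 1.4.2.2.1 gives, for INC424, 32.4% with thrombocytopenia needing dose reduction or interruption. Grade 3 or 4 thrombocytopenia was 64.2% with baseline platelets 100 to 200 and 35.4% above 200. Neutropenia led to a hold or reduction in 1.3%. Table 1-3 gives LDE225-related grade 3/4 AST in 4/103 = 3.9% and ALT in 3/103 = 2.9%, with 0/26 for each at 800 mg QD. None of these isolates grade 4 events.

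**The case against.** The best reply is that the protocol does say where to look. The chain from Section 6.3.1 through 6.2.5.1 and 6.3.2 ends at Table 6-6, whose title names exactly these patients. Table 6-6 also sits inside Section 6.3.1, so the pointer in 6.2.5 reaches both tables. A reader might infer that the protocol leaves the choice of table wholly open; the cross-references do not support that. What stands is that no sentence ranks the tables, and the Table 6-4 rows keep a different dose.

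Five disagreeing bands might also be read as five collisions. Four are hold versus permitted restart, and the Table 6-6 title allows it to be read there as a ceiling. No harm is shown at those counts: for lesser cytopenias Table 6-4 itself allows INC424 up to 10 mg BID at platelets 50 to <75 and full dose of both drugs at grade 3 neutropenia.

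Two other strong readings fail. The thrombocytopenia rates do not show that the grade 4 restart is common, because they mix grades; at most they bear on the grade 3 row. And not every 5 mg BID dose breaches the floor, because level -1 is a combination.

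Sponsor consultation is required before resuming after a DLT, so one party should see these restarts. That reduces variation between sites, but does not settle which written rule applies. SAP Section 1.1 records that Stage 2 will not enroll; treated patients may still continue for at least two years and into the extension, so the rules remain in use.

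**Conclusion.** The concern holds in limited form. There is one firm contradiction in restart dose: after grade 4 thrombocytopenia, at platelets 75 to <100, for patients originally on INC424 15 or 20 mg BID. At the recommended Phase II dose it is twofold. Four further bands differ on hold versus restart. The grade 4 AST/ALT row contradicts a mandatory stop, and the structure of Section 6.2.5 favours the stop. The floor conflict is clean only for patients already at dose level -1.

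This rests on the current protocol text and on grade 1 as Table 6-4 defines it. How many patients would be affected cannot be derived from the documents. A reader might infer bias in the spleen-response endpoint, but nothing in the documents supports such a claim, and no effect on power or error rate follows. The correction should be made on safety grounds.

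**What to change.** 1. In the Table 6-4 grade 4 neutropenia and thrombocytopenia rows, replace the instruction to maintain the dose with a restart per Table 6-6, and state in Section 6.3.1 that Table 6-6 governs. If the stricter hold to grade 1 is wanted, raise the thresholds within Table 6-6.
2. Align the Table 6-4 grade 4 AST/ALT row with the mandatory stop in Sections 6.2.5 and 7.1.3. Add an AST/ALT exception to those bullets only if the clinical team justifies it; the documents alone do not support loosening the stop.
3. In Section 6.3.1, Section 7.1.3 and the Table 6-2 footnote, name INC424 5 mg BID for grade 3 thrombocytopenia and for the Table 6-6 restart as exceptions to the floor.
4. Change the febrile neutropenia bullet in Section 6.2.5 to any episode of grade ≥3, matching Table 6-4 and Section 7.1.3.

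The cost is amendment wording and a clarification letter to sites; no new procedures or data are needed.

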Appropriate eligibility criteria and specific DLT definitions, as well as specific dose modification and stopping rules are included in this protocol.

Patients who experience a DLT will have their therapy with LDE225 and INC424 interrupted and will be followed as described in [Table 6-4](#). After recovery from the toxicity in question, if the Investigator believes that it is in the patient's best interest to resume therapy with LDE225 and INC424, the patient may resume therapy, only after consultation with the Sponsor, according to the guidelines described in [Section 6.3.1](#) and [Table 6-4](#).

However, the patient must be permanently discontinued from study medication and withdrawn from the study, if any of the following DLTs occur:

- any grade ≥ 3 hemorrhagic event
- grade 4 anemia for ≥ 7 consecutive days despite PRBC transfusions
- 2nd episode of grade ≥ 3 febrile neutropenia
- grade 3 renal toxicity for ≥ 7 consecutive days
- grade 4 renal toxicity
- grade 4 non-hematologic toxicity

If during the first 6 weeks a patient misses > 10 doses of LDE225 or > 20 doses of INC424, the patient will not be evaluable for DLTs. The patient can continue in the study, but another patient has to be enrolled at the same dose level in order to reach the required minimum number of patients in the cohort.

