6.3 Dose modifications

6.3.1 Dose modification and dose delay

For patients who do not tolerate the protocol-specified dosing schedule, dose adjustments are permitted in order to allow the patient to continue the study treatment. The following guidelines need to be applied. Any plan to deviate from these guidelines in view of patient safety must be discussed with the sponsor unless there is an urgent need for action.

All dose modifications should be based on the worst preceding toxicity as graded by the NCI Clinical Toxicity Criteria (NCI-CTCAE version 4.03). If study treatment is held due to toxicity, scheduled visits and all assessments as described in [Table 7-1](#) should continue as scheduled, except without dosing. Dose modification guidelines are described in [Table 6-4](#).

If an adverse event is clearly associated to one of study drugs, the dose adjustment directed for that study drug will be followed; however, if the causality is not clear, then it may be necessary to adjust both study drugs. Dosing adjustments will be discussed with the sponsor.

If a patient experiences a DLT then treatment with LDE225 plus INC424 must be stopped and the patient may be discontinued from the study. However, following resolution of the DLT to CTCAE grade 1 or to the patient's baseline value, the patient may continue to receive study treatment at a reduced combination dose level, if appropriate, at the discretion of the investigator and after discussion with the Sponsor.

For each patient, a maximum of 2 dose reductions will be allowed, after which the patient will be required to discontinue study treatment. If the same toxicity returns after re-initiation of treatment at the same dose level, the second re-initiation must resume at a lower dose level. The patient must also discontinue study treatment if, after the treatment is resumed at the lower dose level, the same toxicity recurs with the same or worse severity (except for thrombocytopenia, anemia and neutropenia).

Dose level (-1) is the lowest acceptable dosing level for a patient participating in the study. If a patient cannot tolerate dose level (-1), then study treatment must be discontinued and the patient must be withdrawn from the study. However, if patients in Cohort 1 experience thrombocytopenic DLTs then patients in dose level (-1) will receive INC424 5mg BID and LDE225 200 mg QD.

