| Febrile neutropenia (Grade \geq 3) (ANC < $1.0 \times 10^9/L$, with a single temperature of ≥ 38.3 °C or a sustained temperature of ≥ 38 °C for more than one hour) | INC424: Discontinue study treatment LDE225: Discontinue study treatment |
| Thrombocytopenia (for 2 consecutive assessments within 48 hrs) | |
| Grade 1 (PLT < LLN - $75 \times 10^9/L$) | INC424: Maintain dose level LDE225: Maintain dose level |
| Grade 2 (PLT < $75 - 50 \times 10^9/L$) | INC424: Reduce to 10 mg BID or continue at same dose level (whichever is lower) LDE225: Maintain dose level |
| Grade 3 (PLT < $50-25 \times 10^9/L$) | INC424: Reduce to 5mg BID LDE225: Maintain dose level |
| Grade 4 (PLT < $25 \times 10^9/L$) | INC424: Hold dose until resolved to \leq grade 1, then maintain dose level LDE225: Hold dose until resolved to \leq grade 1, then maintain dose level |
| Hemorrhagic event of any kind (if related to study treatment) | |
| Grade 1 | INC424: Maintain dose level LDE225: Maintain dose level |
| Grade 2 | INC424: Hold dose until resolved completely, then \downarrow by 5 mg BID LDE225: Hold dose until resolved completely, then maintain dose level |
| Grade 3 or 4 | INC424: Discontinue study treatment LDE225: Discontinue study treatment |
| RENAL | |
| Serum creatinine | |
| < 2 x ULN | INC424: Maintain dose level LDE225: Maintain dose level |
| 2 – 3 x ULN | INC424: Hold dose until resolved to \leq grade 1, then: If resolved in \leq 7 days, then maintain dose level If resolved in > 7 days, then \downarrow by 5 mg BID LDE225: Hold dose until resolved to \leq grade 1, then: If resolved in \leq 7 days, then maintain dose level If resolved in > 7 days, then \downarrow 1 dose level |
| Grade 3 (> $3.0 - 6.0 \times ULN$) | INC424: Discontinue study treatment LDE225: Discontinue study treatment |
| Grade 4 (> $6.0 \times ULN$) | INC424: Discontinue study treatment LDE225: Discontinue study treatment |

| | |
|--|---|
| Dose modifications for toxicities occurring during the DLT-definition period (6 weeks or 42 days), and considered as treatment-related, will not be allowed until the toxicity qualifies as a DLT. | |
| Worst toxicity (CTCAE 4.03 Grade) | Dose Modifications for INC424 and LDE225 |
| HEPATIC | |
| Bilirubin (*for patients with Gilbert Syndrome these dose modifications apply to changes in direct bilirubin only). Bilirubin will be fractionated if elevated | |
| Up to 2.0 x ULN | INC424: Maintain dose level LDE225: Maintain dose level |

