6.3.2.2 Management of neutropenia

In the case of grade 4 neutropenia, assessment of ANC count is recommended to be repeated at least twice a week until resolution to grade ≤ 3 neutropenia.

Dose restart guidelines and allowed maximum doses for patients who have previously interrupted dose for grade 4 neutropenia can be found in [Table 6-6](#).

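### After Grade 4 thrombocytopenia or neutropenia, Tables 6-4 and 6-6 give different restart thresholds and INC424 restart doses, and the protocol does not say which prevails

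*Protocol*

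**What the plan says.** Both tables sit in Protocol Section 6.3.1.

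- **Table 6-4, Grade 4 neutropenia and Grade 4 thrombocytopenia rows.** Both drugs are held until grade 1 or better and then resumed at the same dose level. Where the INC424 entry runs into the LDE225 entry, the text reads "grade 1, then maintain dose level LDE225: Hold dose until resolved to". The table's own limits put grade 1 at ANC 1.5 or above and platelets 75 or above.
- **Table 6-6, titled for patients interrupted for those same two toxicities.** INC424 restarts at 5 mg BID from platelets 50 or ANC 0.5, and at the original dose from platelets 100 or ANC 1. At platelets 75 to below 100 the entry is "Restart at 10 mg BID for at least 14 days If stable, may increase to 15 mg BID or original dose, (whichever is lower"), and at ANC 0.75 to below 1 it is "10 mg BID for at least 2 weeks; if stable, may increase to 15 mg BID or original dose, (whichever is lower"). LDE225 restarts at its original level in every band from platelets 50 or ANC 0.5 upward.

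The cross-references run to both tables:

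- **Section 6.2.5:** for resumption after a DLT the places named are Section 6.3.1 and Table 6-4, with the words "the patient may resume therapy, only after consultation with the Sponsor, according to the guidelines described in". Under Table 6-3, a Grade 4 platelet or neutrophil count on two consecutive assessments is a DLT.
- **Section 6.2.5.1:** the reader is sent to Section 6.3.2, with the words "Additional guidance on the management of grade 4 thrombocytopenia and grade 4 neutropenia is described in".
- **Sections 6.3.2.1 and 6.3.2.2:** both point to Table 6-6, the first with "Dose restart guidelines and allowed maximum doses for patients who have previously interrupted dose for grade 4 thrombocytopenia can be found in", the second with "Dose restart guidelines and allowed maximum doses for patients who have previously interrupted dose for grade 4 neutropenia can be found in".
- **Section 6.3.1 text:** the DLT must first have resolved to grade 1 or to baseline. Someone in that position "may continue to receive study treatment at a reduced combination dose level, if appropriate, at the discretion of the investigator"; sponsor discussion is also required.
- **Table 6-7:** after a hematologic DLT, counts are checked at least twice weekly until grade 1 or better, then at least weekly until treatment starts again or the count stabilizes.

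**The concern.** Two explicit safety rules cover the same event in the same patients and give different instructions. They disagree on when to restart and, at one platelet level, on how much INC424 to give. Section 6.2.5.1 calls Section 6.3.2 additional guidance and does not say that it overrides Table 6-4.

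What is at stake is INC424 re-exposure after a Grade 4 cytopenia. Section 1.1 names thrombocytopenia as a DLT of INC424, and 20 mg BID, where the dose gap is widest, is the INC424 component of the confirmed RPIID (Amendment 2 rationale). The chosen table also affects how long a patient is off drug. Sections 6.3.1 and 7.1.3 require discontinuation after more than 21 days of interruption, unless the patient is benefiting and the sponsor and investigator discuss it.

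**Working it through.** The plan states no figure to reproduce, so the check sets the two rules side by side.

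**Inputs.** Table 6-4 rule: hold below platelets 75 or ANC 1.5, otherwise resume the original dose. Table 6-6 rule: as printed for its ten count bands (five platelet, five ANC).

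| Current count (x10^9/L) | INC424, Table 6-4 | INC424, Table 6-6 | LDE225, 6-4 / 6-6 |
|---|---|---|---|
| Platelets <50 | hold | hold | hold / hold |
| Platelets 50 to <75 | hold | 5 mg BID | hold / original |
| Platelets 75 to <100 | original | 10 mg BID | original / original |
| Platelets 100 to <125 | original | original | original / original |
| Platelets ≥125 | original | original | original / original |
| ANC <0.5 | hold | hold | hold / hold |
| ANC 0.5 to <0.75 | hold | 5 mg BID | hold / original |
| ANC 0.75 to <1 | hold | 10 mg BID | hold / original |
| ANC 1 to <1.5 | hold | original | hold / original |
| ANC ≥1.5 | original | original | original / original |

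**Threshold.** Four bands differ for both drugs, always as hold against treat: platelets 50 to <75, and the three ANC bands from 0.5 to <1.5. Table 6-4 is the stricter table in all four. The Section 6.3.1 text sides with Table 6-4 by requiring grade 1 or baseline, and the monitoring sequence in Table 6-7 implies the same order. The baseline alternative does not explain the lower Table 6-6 bands, because entry required platelets of at least 75 and ANC above 1.5 (Section 5.2).

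**Dose.** One further band, platelets 75 to <100, differs for INC424 only. Daily dose is twice the BID dose:

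- Original 20 mg BID: 2 x 20 = 40 mg/day (Table 6-4) against 2 x 10 = 20 mg/day (Table 6-6) for at least 14 days, then at most 2 x 15 = 30 mg/day.
- Original 15 mg BID: 2 x 15 = 30 against 20 mg/day.
- Original 10 mg BID: 2 x 10 = 20 against 20 mg/day, so no difference.

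Here Table 6-4 gives more drug, so neither table is the more cautious throughout for patients on 15 or 20 mg BID.

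**Totals.** INC424 differs in 4 + 1 = 5 of 10 bands at an original 15 or 20 mg BID and in 4 of 10 at 10 mg BID. LDE225 differs in 4 of 10.

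**Can the tables be read in sequence?** If Table 6-6 applied only once the Table 6-4 hold had ended, its restart entries below platelets 75 and ANC 1.5 could never be used for a Grade 4 restart. If Table 6-6 replaces Table 6-4, the explicit Grade 4 rows of Table 6-4 are wrong.

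**The case against.** The best defence is that the tables can be reconciled in practice. Table 6-6 is titled as giving allowed maximum doses, so a site that keeps holding below grade 1 exceeds nothing in it. At platelets 75 to <100, a site can restart at 10 mg BID and rely on the optional post-DLT reduction in Section 6.3.1. A reader might infer from the two tables that a site cannot comply with both. The documents do not support that, because taking the lower dose band by band is workable. It is nevertheless an unstated reading, and a site that follows Table 6-4 alone gives the higher INC424 dose.

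A second defence is that the specific restart table should govern, since Sections 6.3.2.1 and 6.3.2.2 name it. The Section 6.2.5 pointer also takes in Table 6-6, because it cites Section 6.3.1 as a whole. That is fair: Section 6.2.5 does not send patients to Table 6-4 alone. But Table 6-4 has its own Grade 4 rows and is named there, and on the threshold Table 6-6 is the outlier. A reader might therefore go too far in concluding that Table 6-6 is simply the right rule.

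Third, there are safeguards. Resumption after a DLT needs sponsor consultation, and a note to Table 6-4 allows case-by-case discussion of a recommendation to keep the same dose. Both help, but neither sets a default.

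Fourth, the band counts overstate the size if read as frequencies. Three of the five INC424 differences concern ANC, and Section 1.4.2.2.1 reports INC424 held or reduced for neutropenia in only 1.3% of Phase III myelofibrosis patients. If that monotherapy rate applied to the 50 patients treated by February 2015, it would be 0.013 x 50 = 0.65 patients. The SAP (Section 1.1) also says Stage 2 will not enroll. These points limit the number affected. They do not remove the conflict for patients still on treatment or in the extension phase.

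**Conclusion.** The inconsistency stands and should be corrected. It has two parts: a restart threshold (platelets 75 and ANC 1.5, against platelets 50 and ANC 0.5), and an INC424 restart dose at platelets 75 to <100 (20 mg/day apart at an original 20 mg BID, 10 mg/day apart at 15 mg BID, none at 10 mg BID). The weight lies on INC424. For LDE225 it is mainly conflicting wording, since Section 2.3 reports no marrow suppression with LDE225 monotherapy.

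This rests on the grade limits printed in Table 6-4, and on reading its instruction to maintain the dose as a return to the dose before interruption. The documents do not give the frequency of Grade 4 interruptions in this trial, so the number of patients affected is unknown. No sample size, power or interim figure is touched.

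**What to change.** State one rule and align every place that describes restart.

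**Option consistent with the Section 6.3.1 text and Table 6-7.** Hold both drugs until grade 1 (platelets at least 75, ANC at least 1.5). Then restart INC424 at the Table 6-6 dose for the current count (10 mg BID at platelets 75 to <100, original dose at 100 or above) and LDE225 at its original level.

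- In Table 6-4, change the INC424 instruction in the Grade 4 thrombocytopenia row to match. The Grade 4 neutropenia row needs no dose change, because both tables give the original dose at ANC 1.5 or above.
- In Table 6-6, change the rows for platelets 50 to <75 and ANC 0.5 to <1.5 to a continued hold for Grade 4 restarts. Limit the change to those restarts, because Section 6.3.2.1 also sends patients whose dose was reduced for thrombocytopenia to this table.
- In Section 6.3.1, add a sentence relating the optional reduced combination level to this rule.

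**If the clinical team intends the earlier Table 6-6 thresholds.** Point both Grade 4 rows of Table 6-4 to Table 6-6, and also amend the grade-1 condition in the Section 6.3.1 text and in Table 6-7. Changing Table 6-4 alone would leave those two places in conflict.

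**Cost.** Either option is protocol wording with no new assessments. The grade-1 option lengthens some holds and may bring patients up against the 21-day limit. Section 1.4.2.2.1 gives a median of 14 days for platelets to recover above 50, so waiting for 75 could plausibly use up that window, though this is inference. The Table 6-6 option re-exposes patients at lower counts.
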